## CHAPTER 5 OBSERVATION FOR RECURRENCE

### 716 5.1 Overview

717

718 Active Treatment Group and Control Treatment Group responders in the randomized trial are  
719 continued in an observation phase for 12 months in order to determine the rate of recidivism  
720 following successful treatment after treatment is discontinued.

721

722 Treatment group responders are patients who improved to 20/25 or better in the amblyopic eye  
723 and maintained or improved the visual acuity in the non-amblyopic eye on treatment, and for  
724 whom the investigator is ready to discontinue all treatment other than spectacles (if prescribed) at  
725 the 17-week visit.

### 726 5.2 Visit Schedule

727

728 Follow-up visits will occur at 13, 26, and 52 weeks  $\pm$  2 weeks timed from the discontinuation of  
729 treatment. Additional visits are at the discretion of the investigator.

### 730 5.3 Examination Procedures

731

732 At each visit, distance visual acuity will be measured in each eye without cycloplegia and with  
733 appropriate refractive correction by the eETDRS testing protocol. There is no masked testing of  
734 visual acuity in the observation phase.

735

736 A refraction should be done at least once during the observation phase of the study.

737

738 At the 13-week and 52-week observation phase visits, the following additional testing will be  
739 done:

- 740 • Measurement of ocular deviation in primary position at distance and near by  
741 Simultaneous Prism and Cover Test (SPCT)
- 742 • Binocularity testing (Titmus Fly and Randot Preschool Test)

### 743 5.4 Recurrences of Amblyopia

744

#### 745 Definition of Recurrence

746 A recurrence of amblyopia is defined as two consecutive visual acuity measurements in the  
747 amblyopic eye that are 10 or more letters worse than the acuity at the time treatment was  
748 discontinued. The two measurements can be made on the same day or on different days.

749

- 750 • Recurrence may be declared at any visit (protocol-specific or additional visit). If at the  
751 52-week observation phase visit, a patient who has not previously been classified as  
752 having a recurrence has a decrease in visual acuity of 10 or more letters (as described  
753 above) on a single measurement and the measurement is not repeated on that day, a  
754 repeat acuity testing on a subsequent day will be considered to be part of this visit.
- 755 • If a refraction has not been performed within the prior six months, as per usual clinical  
756 practice it should be repeated before retesting acuity and classifying a patient as having a  
recurrence.

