**508 3.1 Randomization Groups**

509

510 Each patient will be randomly assigned to one of two treatment groups in a 1:1 ratio:

- 511 1. Two (2) hours of daily patching combined with 30 minutes of daily near activities at  
512 home, 30 minutes of daily at-home active vision therapy, and a weekly 45 minute in-  
513 office active vision therapy session.
- 514 2. Two (2) hours of daily patching combined with 30 minutes of daily near activities at  
515 home, 30 minutes of daily at-home control vision therapy, and a weekly 45 minute in-  
516 office control vision therapy session.

517

518 Spectacle wear will be continued if prescribed. Patients wearing contact lenses must be switched  
519 to spectacles prior to enrollment for the duration of the study.

520

521 Weekly Office Visits: Each patient randomized into the study will be seen on a weekly basis for  
522 administration of treatment for 16 weeks. At each office visit, the patient will be queried  
523 regarding diplopia and visual acuity in each eye will be measured using the eETDRS protocol.  
524 Each group will receive 45 minutes of vision therapy activities dependent upon their group  
525 assignment.

526

527 Daily patching and at-home vision therapy will be continued through the 17 week masked  
528 examination.

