#### *Observation phase sample size*

Based on the responder rates assumed for the trial sample size calculation, it is expected that  $111 \times 0.30 = 33$  patients from the control group and  $111 \times 0.50 = 56$  patients from the active VT group will be eligible for the observation phase, for a total of 89 patients. However, patients who drop out of the trial prior to completion will not be available for enrollment into the observation phase, and additional patients may drop out during the observation phase. Assuming that 20% of observation phase-eligible patients drop out at any stage of the trial, about 70 patients will have complete observation phase data; of these, 44 will be from the active VT group and 26 from the control group.

974 The primary goal of this phase will be to estimate the proportion of patients with recurrence of  
975 amblyopia (as defined in protocol section 5.1.4) during the 1 year observation phase. Based on  
976 data from ATS3, the expected proportion with recurrence in the control group is 7%. If the  
977 recurrence in the VT study is similar, the expected width of the 95% confidence interval on the  
978 recurrence proportion will be  $\pm 8\%$  for the active VT group,  $\pm 11\%$  for the control group, and  
979  $\pm 7\%$  for both groups combined.

980

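### The one week-17 score that makes a child a responder is also the reference for the 10-letter recurrence rule, so that reference is biased high and some stable children can be classed as recurrences

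*Protocol*

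**What the plan says.** - **Entry to observation (section 5.1).** "Treatment group responders are patients who improved to 20/25 or better in the amblyopic eye", with sound-eye acuity maintained or improved, and for "whom the investigator is ready to discontinue all treatment other than spectacles (if prescribed) at" the 17-week visit.
- **When treatment stops (section 3.1).** "Daily patching and at-home vision therapy will be continued through the 17 week masked" examination. Acuity at discontinuation is therefore the week-17 acuity.
- **How it is measured (section 4.2.3).** The masked examination lists one eETDRS measurement per eye and describes no retest.
- **Recurrence (section 5.4).** "A recurrence of amblyopia is defined as two consecutive visual acuity measurements in the" "amblyopic eye that are 10 or more letters worse than the acuity at the time treatment was" discontinued. "The two measurements can be made on the same day or on different days", and "Recurrence may be declared at any visit (protocol-specific or additional visit"). A refraction should be repeated first if none was done in the prior six months.
- **Planning (section 8.1, observation phase sample size).** Estimating the recurrence proportion is the primary goal of this phase. On "data from ATS3, the expected proportion with recurrence in the control group is 7%. If the" trial behaves similarly, half-widths of 8, 11 and 7 points are expected for 44 active, 26 control and 70 combined patients. Section 8.5 plans a Kaplan-Meier estimate overall and by group.

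**The concern.** One score does two jobs. It admits the child because it is high, and it is then the level from which loss is counted. With any non-zero measurement error, the scores that clear a cut-off exceed the true acuities behind them on average. Even without selection, a reference resting on one test passes its whole error into every later comparison.

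The safeguards (the 10-letter threshold, the second measurement, the repeat refraction) all act at follow-up. None corrects a reference that is too high. There are at least three occasions on which a stable child can meet the rule. At stake is how much of the reported recurrence proportion is real loss and how much is measurement artefact.

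**Working it through.** **The plan's own figure first.** Take X ~ Binomial(n, 0.07) and average the half-width of the exact 95% interval over X. This gives 8.4 points (n = 44), 11.2 (n = 26) and 6.6 (n = 70), which agrees with the stated 8, 11 and 7. Expected recurrences among completers are 70 × 0.07 = 4.9.

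**Inputs from the protocol.** Responder rates 30% (control) and 50% (active), section 8.1. 20/25 = 79 letters, from the sound-eye criterion in section 1.3. Three scheduled visits, section 5.2. Loss of 10 or more letters on two measurements, section 5.4.

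**Assumed, not in the protocol.** SD of true week-17 acuity 8 letters; single-test error SD s from 2.5 to 5 letters; independent errors; two tests at each visit; true acuity unchanged after week 17, so that every recurrence is false.

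**Excess of the reference.** With observed SD = √(8² + s²), p the responder rate and z the normal quantile for 1 − p:

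mean excess = (s² / SD_obs) × φ(z) / p

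For s = 4, SD_obs = √80 = 8.94.
- Control: (16 / 8.94) × 0.348 / 0.30 = 2.1 letters.
- Active: (16 / 8.94) × 0.399 / 0.50 = 1.4 letters.

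**False recurrence over three visits (simulation), control / active.** The middle column uses one separate score that played no part in selection. The last uses the mean of the week-17 score and one independent on-treatment score.

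| s (letters) | Excess | Week-17 reference | Separate single score | Mean of two |
|---|---|---|---|---|
| 2.5 | 0.9 / 0.6 | 0.1% / 0.1% | 0.05% | 0.0% / 0.0% |
| 3 | 1.2 / 0.8 | 0.7% / 0.5% | 0.3% | 0.1% / 0.1% |
| 3.5 | 1.6 / 1.1 | 2.1% / 1.6% | 1.0% | 0.3% / 0.3% |
| 4 | 2.1 / 1.4 | 4.7% / 3.5% | 2.1% | 1.1% / 0.9% |
| 5 | 3.1 / 2.1 | 12% / 9% | 5.4% | 4.1% / 3.3% |

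**Share due to selection.** At s = 4: control (4.7 − 2.1) / 4.7 = 55%; active (3.5 − 2.1) / 3.5 = 40%. The remainder is ordinary noise in a one-score reference.

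**In children.** At s = 3.5: 26 × 0.021 + 44 × 0.016 = 1.3 false recurrences among 70. At s = 4: 26 × 0.047 + 44 × 0.035 = 2.8. At s = 2.5: fewer than 0.1. All are to be set beside the 4.9 expected.

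**Sensitivity.** At s = 4, changing the true SD from 6 to 10 letters moves the control rate only from 5.2% to 4.3%. Correlated errors within a visit, plausible for same-day repeats, matter more: with the observed SD held at 8, s = 3.5 and correlation 0.5, the expected number rises from 1.3 to 2.7. Extra visits would also raise it.

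**The case against.** The case on the other side is about size, attribution and remedy, and much of it stands.

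- **Size.** The protocol gives no test-retest error, and below about 2.5 letters the effect vanishes. An SD of 5 implies a test-retest difference with SD √2 × 5 ≈ 7 letters, which sits awkwardly with a protocol that treats one logMAR line as real improvement when judging stability (section 2.3). The upper end of the range should carry little weight.
- **The 7%.** A reader might infer that a fixed part of the observed recurrence is artefact on top of 7%. The documents do not support that. The 7% comes from the earlier trial; if it was measured against a similar reference, which the protocol does not say, it already contains the artefact.
- **Attribution.** A reader might put the whole false rate down to regression to the mean. Only about half is.
- **Arms.** A reader might conclude that the two recurrence estimates cannot be set side by side. At s = 4 the gap is 4.7 − 3.5 = 1.2 points, about 0.3 of a child among 26 controls, against planned half-widths of 8 and 11 points. No between-group test of recurrence is planned, and the gap arises only if responder rates differ.
- **Entry is not purely one score.** Sound-eye acuity and the investigator's readiness to stop treatment also count. This may soften the selection, but the amblyopic-eye cut-off still rests on one test.
- **Remedy.** Section 5.5 ties retreatment to meeting the recurrence criteria, so rewriting the definition in section 5.4 would alter clinical management. That objection is right, and it confines the fix to the analysis.

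What the objection does not remove is the mechanism or its direction.

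**Conclusion.** The point holds as a minor design weakness. The protocol uses one week-17 score both to select responders and as the recurrence reference, so the reference is too high on average and some stable children can be counted as recurrences despite the two-measurement rule. Mechanism and direction follow from the text for any non-zero measurement error.

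The size is conditional on an error SD that the documents do not give: negligible at 2.5 letters, about a quarter to a third of the 7% planning figure at 3.5, and half to two thirds of it at 4. These figures rest on independent errors, three visits and a true SD near 8 letters. The observation phase is descriptive, the difference between arms is small beside the planned precision, and the 17-week primary comparison is untouched.

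**What to change.** In section 8.5, add a second classification of recurrence for the analysis. Set the reference to the mean of the week-16 and week-17 amblyopic-eye eETDRS scores, using week 17 alone if week 16 is missing, and report this estimate beside the one that uses the week-17 reference. State that it applies to the analysis only and that the criteria used by section 5.5 for retreatment are unchanged.

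No new test is needed: weekly visits already use the eETDRS protocol (section 3.1.1). In the simulation the averaged reference cuts false recurrence by about two thirds or more. It still includes the selecting score, so about half of the mean excess remains.

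Costs:
- The week-16 score may come from an unmasked tester, although observation-phase acuity is unmasked anyway (section 5.3).
- Detection of a true loss of exactly 10 letters falls by about 2 to 7 points (at s = 4, from 72% to 67% in controls). Detection of a 15-letter loss stays about the same or improves slightly.
- The averaged figure is less comparable with the earlier trial's 7%, which is why both should be reported.

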### 757 5.5 Treatment of Amblyopia Recurrence

758

759 If amblyopia recurs and meets the study's recurrence criteria, the investigator may institute any  
760 form of amblyopia therapy, which will be recorded on the follow-up exam form. If an

761 investigator believes that treatment should be reinstated but the patient has not met the study's  
762 recurrence criteria, a Protocol Chair should be contacted to discuss the case.  
763  
764 Patient follow up will continue through the close-out visit, with collection of treatment and  
765 acuity data.  
766

## 767 **CHAPTER 6 CONTROL NON-RESPONDERS ELECTING ACTIVE VISION THERAPY**

### 768 **6.1 Overview**

769

770 Patients in the control treatment group who are classified as a non-responder at the 17-week  
771 masked outcome examination will be offered a course of active vision therapy. If the  
772 patient/parents elect the additional therapy within 10 days after the completion of the 17-week  
773 masked examination they will follow the same course of treatment as the active group. During  
774 this additional treatment they will be considered to be in the study and the therapy will be paid  
775 for by the study. An outcome examination mirroring the 17-week masked examination will be  
776 performed at the completion of active therapy.

777

778 The goal of this phase is to estimate the proportion of control patients who meet criteria for  
779 treatment success at the end of the course of active therapy. Although it will not be possible to  
780 attribute improvement to active therapy versus increased time on patch, this will allow an  
781 assessment of what proportion of patients benefit from increased time on treatment that includes  
782 vision therapy.

### 783 **6.2 Start of Additional Therapy**

784

785 Once patients elect to undergo the additional treatment they will be required to begin the active  
786 therapy within 21 days after the primary outcome examination.

### 787 **6.3 Weekly In-Office Vision Therapy Visits**

788

789 The following activities/testing will be performed at the weekly office visits in the specified  
790 order:

- 791 • Binocular diplopia query
- 792 • If a patient reports the onset of constant diplopia, treatment will be discontinued. If  
793 diplopia has resolved at the next week's office visit, therapy will be reinstated;  
794 however, anti-suppression therapy will not be performed during the rest of the therapy
- 795 • Measurement of visual acuity in each eye by the eETDRS testing protocol on the  
796 Electronic Visual Acuity Tester (performed only at the 7 and 8 week treatment visits)
  - 797 ○ The right eye is tested first, then the left eye
  - 798 ○ Testing is performed without cycloplegia with spectacles (if worn)
- 799 • In-Office Vision Therapy
  - 800 ○ Active vision therapy will be completed each week. The therapist will follow the
  - 801 Manual of Procedures for the Active Vision Therapy.
- 802 • Completion of the therapy progress checklist

803

804 All patients will continue to have weekly in-office treatment sessions even if the visual acuity  
805 reaches 20/20 during the study.

806

807 All procedures at weekly vision therapy visits are permitted to be performed by a person who is  
808 unmasked to the patient's treatment assignment.

### 809 **6.4 Scheduling of Weekly In-Office Vision Therapy Visits**

810

811 Ideally, treatment visits should be exactly 7 days apart; however, this will not always be possible.  
812 As such, we have established acceptable visit windows for the time between each in-office vision

813 therapy visit. The acceptable window for each appointment is +/-4 days from the original  
814 targeted date (as calculated from the initial therapy session). Furthermore, no more than two  
815 appointments can be scheduled within a 7 day period and successive appointments must be more  
816 than 2 days apart.

817  
818 Coordinators and Vision Therapists should consider creating a standing appointment time for  
819 each patient during the study. Care should be given to not schedule study patients back to back  
820 if possible to help minimize potential interaction between patients in different treatment arms.

## 821 **6.5 17-Week Outcome Examination**

822

823 The following procedures will be performed at a 17-week Outcome Examination. The order of  
824 procedures will be:

- 825 1. Binocular diplopia query
- 826 2. Measurement of visual acuity in each eye by the eETDRS testing protocol on the  
827 Electronic Visual Acuity Tester. (The right eye is tested first.)
- 828 3. Titmus Fly and Randot Preschool Stereoacuity Test
- 829 4. Ocular alignment by SPCT

830

831 The examiner need not be masked to the treatment.

832

833

**835 7.1 Patient Withdrawals**

836

837 A patient (and in this case the parent or guardian) may withdraw from the trial at any time. This  
838 is expected to be a very infrequent occurrence in this trial in view of the similarity of study  
839 procedures to routine clinical practice. If the parent or guardian indicates that he/she wants to  
840 withdraw the child from the study, the investigator personally should attempt to speak with  
841 him/her to determine the reason.

**842 7.2 Risks**

843

844 There are no risks involved in this study that would not be part of usual care. The risks involved  
845 in this study are identical to those for patients treated with the study treatments who do not  
846 participate in the study.

**847 7.2.1 Risk of Patching**

848 In view of the small number of hours of daily patching, significant skin irritation is unlikely. If  
849 irritation occurs, the parent will be advised to put an emollient on the skin and discontinue use of  
850 the patch for a day.

851 ➤ If a skin reaction to the patch occurs, or an allergic reaction occurs serious enough to  
852 discontinue patching, the investigator should call his or her assigned Steering Committee  
853 member to discuss the case. An alternative adhesive patch may be tried. If patching with  
854 adhesive patches is discontinued, then the patient should be tried with a felt “Patch  
855 Works” type patch placed on the lens of the glasses over the non-amblyopic eye (or on  
856 plano lens if patient not wearing spectacles).

857

858 Patching potentially could decrease the visual acuity in the sound eye, although this is almost  
859 always reversible. This occurrence is extremely unlikely in view of the age of the patient and the  
860 small number of hours of daily patching. The diagnosis and management of reverse amblyopia  
861 is left to the investigator’s judgment.

862

863 Patching could precipitate the development of a manifest ocular deviation. If treatment  
864 precipitates the development of a strabismus (e.g., esotropia in child with hyperopia), the parent  
865 will be advised to have the patient see the investigator as soon as possible. The decision to  
866 continue or discontinue therapy will be left to the discretion of the investigator and parent. If the  
867 decision is made to continue treatment, the patient will remain in their assigned group.

868

869 There are some activities that should not be performed when patched due to the level of vision in  
870 the amblyopic eye and some reduction in visual field. These activities include riding a bike, in-  
871 line skating, skateboarding, or other activities in which the child could get hurt. The consent  
872 form will explicitly instruct parents not to allow their child to perform such activities while  
873 patched.

**874 7.2.2 Risk of Examination Procedures**

875 The procedures in this study are part of daily ophthalmic practice in the United States and pose  
876 no known risks. As part of a routine usual-care exam, the patient may receive  
877 cycloplegic/dilating eye drops.

878 **7.2.3 Diplopia**

879 Amblyopia therapy could induce diplopia through occlusion of the dominant eye and disruption  
880 of habitual suppression of the non-dominant eye during binocular conditions. In a study of 404  
881 patients in this age group using patching and atropine eye drops, but without vision therapy,  
882 there were no cases of permanent constant diplopia. Four patients not reporting diplopia at the  
883 outset reported it during follow up, with 3 resolving by the last visit and 1 reporting it  
884 intermittently.[1] Although rare, it is possible that the diplopia could persist even after treatment  
885 is discontinued. Data on the frequency of this complication will be collected as part of the study.

886 **7.2.4 Intercurrent Events**

- 887 1. If visual acuity should worsen in the amblyopic eye (or in the sound eye and does not recover  
888 with cessation or reversal of treatment), the investigator should evaluate this condition using  
889 best clinical judgment and perform whatever work up is clinically indicated to assess for an  
890 alternate cause (other than amblyopia) for the visual loss. Patients found to have a cause  
891 other than amblyopia that fully explains the visual loss (i.e., amblyopia was never present)  
892 will be dropped from the study.
- 893 2. Eye injuries or the development of an eye problem that might affect vision will be reported  
894 on the Follow-up Examination Form. Likewise, the development of a serious medical  
895 problem that might affect the patient's study participation will be recorded.
- 896 3. Patients developing a new, constant tropia should continue on their assigned treatment. The  
897 therapist will eliminate elements of the therapy that would be inappropriate for a child with  
898 constant tropia. However, these patients are still considered as enrolled in the study and  
899 included in the primary outcome analysis. Thus, every attempt should be made to complete  
900 the masked outcome assessment at 17 weeks. Investigators should contact a protocol chair to  
901 discuss these cases as they arise.

902 **7.3 Reporting of Adverse Events**

903  
904 Each investigator is responsible for informing his/her IRB of serious treatment-related adverse  
905 events and for abiding by any other reporting requirements specific to his or her IRB.

906 **7.4 Patient Payments**

907  
908 Patient payments include a \$5 gift certificate given to the child at the end of each weekly office  
909 visit, and monthly check for \$20 for each completed in-office visit to defray travel costs to be  
910 issued to the parent. If there are extenuating circumstances, and the patient is unable to complete  
911 study visits without additional funds due to travel costs, additional funds may be provided.

912 **7.5 Discontinuation of Study**

913  
914 The study may be discontinued by the Steering Committee (with approval of the Data and Safety  
915 Monitoring Committee) prior to the planned completion of enrollment and follow up for all  
916 patients.

917 **7.6 Contacts by the Jaeb Center for Health Research (JCHR)**

918  
919 The JCHR serves as the PEDIG Coordinating Center (CC). The CC will be provided with the  
920 parent/guardian's contact information. The CC staff may contact the parent/guardian during the  
921 study to answer any questions and discuss any problems during the study. Permission for such  
922 contacts will be included in the Informed Consent Form. A patient newsletter, study updates,

923 and a study logo item may be sent. Patients will be provided with a summary of study results in  
924 a newsletter format after completion of the study by all patients.  
925

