## 457   **2.4 Examination Procedures**

### 458   **2.4.1 Historical Information**

459   Historical information to be collected will include: date of birth, gender, race, ethnicity, prior  
460   amblyopia therapy (e.g., glasses, patching, pharmacologic, filters, vision therapy), refractive  
461   correction, and history of allergy/intolerance to bandage adhesive.

462 **2.4.2 Clinical Testing for Enrollment**

- 463 1. Visual acuity in each eye (right eye first) is measured by the ATS single-surround eETDRS  
464 testing protocol on the Electronic Visual Acuity Tester. The protocol for conducting the  
465 visual acuity testing is described in the ATS Testing Procedures Manual. Aspects of the  
466 testing protocol that are specific to this study are indicated below:
- 467 • Testing must be done without cycloplegia (with spectacles, if worn) no more than 7 days  
468 prior to randomization.
  - 469 • Because the patient needs to be wearing spectacles that provide best visual acuity to be  
470 enrolled, trial frames/phoropter with a different correction cannot be used to measure  
471 acuity at enrollment.
  - 472 • If the patient has difficulty with the acuity testing, often he or she will perform better  
473 when the testing is repeated. At the investigator's discretion, acuity can be retested on  
474 the same or a subsequent day to assess eligibility.
- 475 2. Ocular motility examination
- 476 • Measurement of predominant alignment by Simultaneous Prism and Cover Test (SPCT)  
477 in primary position at distance and near.
  - 478 • Testing must be done without cycloplegia (with spectacles if worn) no more than 7 days  
479 prior to randomization
- 480 3. Ocular examination as per investigator's clinical routine to rule out a cause for reduced visual  
481 acuity other than amblyopia
- 482 ➤ if performed within prior 6 months, does not need to be repeated at time of  
483 enrollment.
- 484 4. Binocularity testing (without cycloplegia): Titmus Fly and Randot Preschool Stereoacuity  
485 test
- 486 5. Cycloplegic refraction using cyclopentolate 1% as per investigator's usual routine
- 487 ➤ if performed within prior 6 months, do not need to repeat at time of enrollment

488 **2.5 Randomization of Eligible Patients**

489  
490 Assuming that visual acuity in the amblyopic eye on the better of the initial or repeat tests is  
491 20/40 to 20/100, inclusive, and acuity in the sound eye is 20/25 or better, the patient will be  

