## 644 **3.3 Home Calendar Logs**

645

646 Parents will record the amount of time the patient wore the patch at home each day.  
647  
648 The calendars will be brought to the weekly office visits and a summary of the data will be  
649 entered onto the study website, along with other data collected at therapy visits.  
650  
651 At each visit, the logs will be reviewed by the therapist and an assessment of patching  
652 compliance recorded on the Follow-up Examination Form.  
653

655 **4.1 Follow-up Schedule**

656

657 All patients will have the following study visits:

- 658 • Weekly office visits  $\pm$  4 days for 16 weeks for administration of in-office vision therapy
- 659 • 17-week masked outcome visit  $\pm$  1 week

660 **4.2 Testing Procedures**661 **4.2.1 Weekly In-Office Vision Therapy Visits**662 The following activities/testing will be performed at the weekly office visits in the specified  
663 order:

- 664 • Binocular diplopia query
  - 665 ○ If a patient reports the onset of constant diplopia, treatment will be discontinued. If
  - 666 diplopia has resolved at the next week's office visit, therapy will be reinstated;
  - 667 however, anti-suppression therapy will not be performed for those assigned to
  - 668 Active vision therapy
- 669 • Measurement of visual acuity in each eye by the eETDRS testing protocol on the  
670 Electronic Visual Acuity Tester
  - 671 ○ The right eye is tested first, then the left eye
  - 672 ○ Testing is performed without cycloplegia with spectacles (if worn)
- 673 • In-Office Vision Therapy
  - 674 ○ Active or Control vision therapy based on randomization
- 675 • Completion of the therapy progress checklist

676

677 All patients will continue to have weekly in-office treatment sessions even if the visual acuity  
678 reaches 20/20 during the study.

679

680 All procedures at weekly vision therapy visits are permitted to be performed by a person who is  
681 unmasked to the patient's treatment assignment.682 **4.2.2 Scheduling of Weekly In-Office Vision Therapy Visits**

683 Ideally, treatment visits should be exactly 7 days apart; however, this will not always be possible.  
684 As such, we have established acceptable visit windows for the time between each in-office vision  
685 therapy visit. The acceptable window for each appointment is  $\pm$  4 days from the original  
686 targeted date (as calculated from the initial therapy session). Furthermore, no more than two  

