## 1018 **8.3 Safety Analysis**

1019

1020 Safety data consisting of the number and proportion of patients in each treatment group  
1021 experiencing the following events will be compiled and included in all reports to the DSMC:

- 1022       • Loss of 2 or more lines in sound eye visual acuity from baseline to the 17-week masked  
1023       exam  
1024       • Development of diplopia at any time during treatment and whether it has resolved by the  
1025       17-week masked exam  
1026       • Development of a new ocular deviation and whether it has resolved by the 17-week  
1027       masked exam

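### No diplopia query is scheduled after completed treatment, so persistence after stopping, a risk that Protocol 7.2.3 names, is captured only briefly and only where constant diplopia ended treatment early

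*Protocol*

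**What the plan says.** Section 7.2.3 (Diplopia) describes therapy-induced diplopia and cites a study of 404 patients in this age group, treated without vision therapy. Four of them developed diplopia; three had resolved by the last visit and one still reported it intermittently. The section continues "Although rare, it is possible that the diplopia could persist even after treatment" is discontinued, and closes with "Data on the frequency of this complication will be collected as part of the study".

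On timing, section 3.1 states "Daily patching and at-home vision therapy will be continued through the 17 week masked" examination, and section 3.2 repeats this for patching. Diplopia is queried at each weekly visit (4.2.1) and at the 17-week examination (4.2.3). Section 4.2.1 adds a rule for constant diplopia: "If a patient reports the onset of constant diplopia, treatment will be discontinued. If" "diplopia has resolved at the next week's office visit, therapy will be reinstated".

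The safety synopsis in section 8.3 lists "Development of diplopia at any time during treatment and whether it has resolved by the" 17-week masked exam.

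Responders then enter observation. Section 5.3 opens "At each visit, distance visual acuity will be measured in each eye without cycloplegia and with" appropriate correction. It adds one refraction during the phase, and alignment and binocularity tests at weeks 13 and 52. It lists no diplopia query.

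**The concern.** A harm that may outlast treatment can be assessed only by asking about it once treatment has ended. The protocol has three visits at the right time, and section 5.3 leaves the question out of all of them, although sections 4.2.1, 4.2.3, 6.3 and 6.5 each list it explicitly.

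Resolved by week 17 and resolved after stopping are different statements. A child with diplopia at the week-17 examination is recorded as unresolved and then not asked again. The active arm includes anti-suppression activities (3.1.2), which the cited study did not use. Investigators and families would therefore want to know how each such case ended.

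**Working it through.** **1. Schedule set side by side**

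| Visit | Section | On study treatment? | Diplopia query listed? |
|---|---|---|---|
| First therapy session | 3.1.7, 4.2.1 | Query precedes therapy | Yes, first item |
| Weekly visits | 4.2.1 | Yes, unless stopped for constant diplopia | Yes |
| 17-week masked exam | 4.2.3 with 3.1, 3.2 | Yes, for completers | Yes |
| Observation, 13/26/52 weeks after stopping | 5.2, 5.3 | No, unless treatment is restarted (5.5) | No |
| Weekly visits, added active course for control non-responders | 6.3 | Yes | Yes |
| Outcome exam of that course | 6.5 with 6.1 | Yes, if the course matches the active arm's, as 6.1 says | Yes |

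No row combines completed treatment with a diplopia query.

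**2. What each kind of case yields after treatment stops**

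- Constant diplopia reported before week 16: treatment stops, status is checked at the next weekly visit, and an unresolved case is asked again at week 17. Off-treatment status is known up to week 17 at most.
- Constant diplopia first reported at week 16: about one week of off-treatment information.
- Any diplopia present at week 17 in a child still on treatment: none.
- Intermittent diplopia at any time: the stopping rule in 4.2.1 is written for constant diplopia only, so the queries are made on treatment and none follows. The one unresolved case in the cited study was of this type.

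**3. How many patients are affected (rates from section 8.1)**

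- Eligible for observation: 111 × 0.30 + 111 × 0.50 = 33.3 + 55.5 = 88.8, which reproduces the stated 89. None has a scheduled query.
- Not in observation: 222 − 89 = 133, or 60%.
- Of these, section 8.1 expects 40 control non-responders to take active therapy; they are queried again under 6.3 and 6.5.
- No further scheduled study visit: 133 − 40 = 93, and 93/222 = 42%.

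**4. Expected number of cases**

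- At the cited rate: 4/404 = 0.99%; 222 × 4/404 = 2.2 cases.
- Unresolved at last visit, at the cited rate: 222 × 1/404 = 0.55 cases.
- The documents give no rate under vision therapy. If the active arm had twice the cited rate (an assumption): 111 × 4/404 + 111 × 8/404 = 1.1 + 2.2 = 3.3 cases.

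**The case against.** The strongest reply is that the protocol does observe persistence where it matters most. Constant diplopia stops treatment, the child is asked again off treatment, therapy resumes only if it has resolved, and 8.3 reports the result. That stands. A reader might infer that persistence cannot be observed in anyone; 4.2.1 contradicts this. The exception is nonetheless limited to constant diplopia and to the weeks before week 17.

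Secondly, the phrase in 7.2.3 about this complication may mean diplopia in general, whose on-treatment frequency is collected. That reading is possible, although the preceding sentence is about persistence. Even so, a case present at week 17 has no recorded outcome.

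Thirdly, the final analysis plan will supersede the synopsis in chapter 8. It can change the table, but it cannot supply data that no visit collects. Section 7.2.4 does have eye problems that might affect vision reported on the follow-up form, and 5.2 allows extra visits. Neither means that each child is asked.

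Three further inferences are tempting and are not supported:

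- That there is no baseline because enrolment testing (2.4.2) has no diplopia query. The query comes first in the order set by 4.2.1, and under 3.1.7 study treatment begins at that first session, with patches and software handed out at its end. This gives a status before study treatment.
- That diplopia is the only potentially lasting harm named. Section 7.2.1 also names reduced sound-eye acuity and a new manifest deviation; 5.3 follows both.
- That all 133 patients outside observation are never asked again. About 40 are expected to be. Their first new query may come up to 21 days after week 17 (6.2), and the protocol does not say whether patching continues in that interval. For the other 93 it does not state when treatment ends, so the accurate description is no further scheduled study visit.

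**Conclusion.** The point holds in limited form. For children who complete treatment, no diplopia query is scheduled afterwards, and the planned summary ends at week 17. Persistence after stopping is captured only in the short term, in those whose treatment was stopped early for constant diplopia.

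The gap covers all of the roughly 89 patients in observation, who do attend off-treatment visits, and about 93 of 222 (42%) who have no further scheduled visit. The roughly 40 who take the added course are asked again, but their last query is again on treatment. These counts rest on the protocol's assumed response rates of 30% and 50% and its expected uptake of about one half.

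With about 2 cases expected, no schedule would give a precise rate of persistence. What is lost is the outcome of individual cases. This is a worthwhile, inexpensive improvement to the safety data and does not affect the primary comparison.

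**What to change.** 1. Section 5.3: add the binocular diplopia query at the 13-, 26- and 52-week visits.
2. For any patient with diplopia at the week-17 or 6.5 examination, or still off treatment because of it, record status after treatment ends at a fixed time, for instance 13 weeks, to match the first observation visit. The coordinating center's existing contact with parents (7.6) can serve for those with no further visit; check that the consent wording covers collecting this by phone.
3. Section 8.3: report, by arm, diplopia present at the last on-treatment visit and diplopia persisting afterwards.

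The cost is one added question at existing visits, a few calls (about 2 patients at the cited rate) and one table row. These changes concern data collection and reporting only; they leave every treatment and stopping rule as written.
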